### **6.11.2. Primary Outcome and Methodology**

Efficacy is not a primary outcome for this study.

### **6.11.3. Secondary Efficacy Outcomes & Methodology**

#### **6.11.3.1. Secondary Efficacy Analyses**

The analysis of secondary endpoints is described in [Table JAIM.6.3](#) and [Table JAIM.6.4](#) and Section [6.4](#).

#### **6.11.3.2. Exploratory Efficacy Endpoints**

Analyses of exploratory efficacy endpoints will be described in a separate SAP.

### **6.12. Health Outcomes/Quality-of-Life Analyses**

Analysis of the health outcomes/quality-of-life measures are described in [Table JAIM.6.4](#) and Section [6.4](#). The descriptions and high level derivations are provided in [Table JAIM.6.3](#).

Additional analyses will be documented in a separate analysis plan.

### **6.13. Bioanalytical and Pharmacokinetic/Pharmacodynamic Methods**

No pharmacokinetic or pharmacodynamic analyses are planned for this study.

### **6.14. Safety Analyses**

Detailed analyses and discussion of Study JAIM safety data are more thoroughly assessed in the context of combining the safety data from the originating studies JAHZ and JAIA with the safety data from Study JAIM. The planned analyses are described in the iSAP.

The safety postbaseline period is defined in [Table JAIM.6.5](#).

**Table JAIM.6.5. Definition of Postbaseline Period**

Analysis Population	Treatment Groups (Short Label)	Postbaseline Time Period
Safety Population	See Table JAIM.6.1	
For all analyses except the “by-visit” continuous analysis: From immediately after first dose of baricitinib in Study JAIM and ending at the earliest of
 
 
• 30 days after last dose date of study drug
 
• the study disposition date, or
 
• the cut-off date if subject is on treatment.
 
 
For the “by-visit” continuous analyses: Includes planned/scheduled measurements after first dose of baricitinib up to last visit, excluding the follow up visit.

### 6.14.1. Adverse Events

For the purposes of the CSR for Study JAIM *alone*, the summaries given in [Table JAIM.6.6](#) are planned.

**Table JAIM.6.6. Summary Tables Related to Adverse Events**

Analysis
Listing of adverse events leading to permanent discontinuation of study drug and discontinuation from the study
Listing of deaths
Listing of SAEs
Listing of Opportunistic Infections
Overview of AEs
Overview of Infections
The number and percentage of patients with TEAE using MedDRA Preferred Term nested within SOC
The number and percentage of patients who permanently discontinued from study drug due to an adverse event (including adverse events that led to death) using MedDRA Preferred Term nested within SOC
The number and percentage of patients reporting SAEs using MedDRA Preferred Term nested within SOC
The number and percentage of patients with at least one temporary interruption of study drug.

Abbreviations: AE = adverse event; PT = Preferred Term; SAE = serious adverse event; SOC = System Organ Class; TEAE = treatment-emergent adverse event.

A treatment-emergent AE (TEAE) is defined as an event that first occurred or worsened in severity after the first dose of study treatment in Study JAIM and on or prior to the last visit date during the analysis period. The analysis period is defined as the treatment period plus up to 30 days off-drug follow-up time.

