The categorical safety measures will be summarized with percentages and incidence rates, where appropriate. The mean changes of the continuous safety measures will be summarized using descriptive statistics.

2. Schedule of Activities

Table JAIM.1. Schedule of Activities

	Baseline	Treatment Phase: Study Drug Administration											Follow-up
Visit Number	V1	V2	V3	V4	V5	V6	V7	V8	V9	V10	V11	ET ^a	V801 ^b
Study Week	W0	W4	W12	W24	W36	W48	W60	W84	W108	W132	W156	Any	W160 or last dose + 4 weeks
Study Day	1	29 ± 4	85 ± 7	169 ± 10	253 ± 10	337 ± 10	421 ± 10	589 ± 14	757 ± 14	925 ± 14	1093 ± 14	Any	Last dose + 28 ± 5 days
Procedure													
Informed consent	X												
Abbreviated patient demographics	X												
Symptom-directed physical examination	X ^c	X	X	X	X	X	X	X	X	X	X	X	X
Weight	X ^c	X	X	X	X	X	X	X	X	X	X	X	X
Waist circumference	X ^c	X	X	X	X	X	X	X	X	X	X	X	X
Vital signs (BP ^d , pulse, temperature)	X ^c	X	X	X	X	X	X	X	X	X	X	X	X
Review JAIM inclusion/exclusion criteria	X												
Adverse events	X ^e	X	X	X	X	X	X	X	X	X	X	X	X
Concomitant medications	X ^f	X	X	X	X	X	X	X	X	X	X	X	X
C-SSRS ^g & Self-Harm Supplement Form	X ^c	X	X	X	X	X	X	X	X	X	X	X	X
Self-Harm Follow-up Form ^h	X ^c	X	X	X	X	X	X	X	X	X	X	X	X
QIDS-SR16 ⁱ	X ^c	X	X	X	X	X	X	X	X	X	X	X	X
Log in IWRS	X	X	X	X	X	X	X	X	X	X	X	X	X
Randomization ^j	X												

	Baseline	Treatment Phase: Study Drug Administration											Follow-up
Visit Number	V1	V2	V3	V4	V5	V6	V7	V8	V9	V10	V11	ET ^a	V801 ^b
Study Week	W0	W4	W12	W24	W36	W48	W60	W84	W108	W132	W156	Any	W160 or last dose + 4 weeks
Study Day	1	29 ± 4	85 ± 7	169 ± 10	253 ± 10	337 ± 10	421 ± 10	589 ± 14	757 ± 14	925 ± 14	1093 ± 14	Any	Last dose + 28 ± 5 days
Investigational product dispensed	X		X	X	X	X	X	X	X	X			
Investigational product returned and compliance assessed		X ^k	X	X	X	X	X	X	X	X	X	X	
Physician-Completed Scales^l													
SLEDAI-2K	X ^c	X	X	X	X	X	X	X	X	X	X	X	X
BILAG2004	X ^c	X	X	X	X	X	X	X	X	X	X	X	X
Physician’s Global Assessment of Disease Activity	X ^c	X	X	X	X	X	X	X	X	X	X	X	X
SLEDAI Flare Index	X ^c	X	X	X	X	X	X	X	X	X	X	X	X
SLICC/ACR Damage Index	X ^c					X					X	X	
CLASI	X ^c	X	X	X	X	X					X	X	X
28-Tender and Swollen Joint Counts	X ^c	X	X	X	X	X	X	X	X	X	X	X	X
Patient-Reported Questionnaires													
Worst Pain NRS ⁱ	X	X	X	X	X	X	X	X	X	X	X	X	X
Worst Joint Pain NRS ⁱ	X	X	X	X	X	X	X	X	X	X	X	X	X
Worst Fatigue NRS ⁱ	X	X	X	X	X	X	X	X	X	X	X	X	X
Patient’s Global Impression of Severity (PGI-S) ⁱ	X	X	X	X	X	X	X	X	X	X	X	X	X

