10.3.4. Safety Analyses

Safety assessments will include AEs, laboratory analytes, vital signs, and questionnaires to assess the existence and severity of depression.

The primary endpoints of safety and tolerability will be analyzed as part of the integrated safety analyses for SLE. All details of these integrated analyses will be contained in the integrated safety analysis plan for SLE.

Categorical safety measures for JAIM alone will be summarized with percentages, and incidence rates where appropriate. The following summaries will be reported specifically for JAIM:

- patients who permanently discontinue from study drug due to adverse events,
- patients reporting SAEs during the treatment period,
- patients with at least 1 temporary interruption of study drug
- patients who permanently discontinued study drug prior to full study completion

Additional details, including any measures that will utilize inferential statistics, will be specified in the SAP and/or iSAP.

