## 6. A Priori Statistical Methods

### 6.1. General Considerations

This Statistical Analysis Plan (SAP) describes analyses that will be utilized for the full clinical study report (CSR) for Study JAIM, at the time of JAIM primary outcome database lock. Analyses to be produced prior to the JAIM primary outcome database lock, for purposes of regulatory submissions, will be identified in the retained list of analyses. Additional safety analyses that integrate data from the originating studies will be specified in the integrated safety analysis plan (ISAP) for SLE. Any exploratory analyses will be described in a separate document. Statistical analysis of this study will be the responsibility of Eli Lilly and Company or its designee.

Not all displays described in this SAP will necessarily be included in the CSR. Not all displays will necessarily be created as a “static” display. Some may be incorporated into interactive display tools such as Spotfire instead of, or in addition to, a static display. Any display described in this SAP and not included in the CSR would be available upon request.

Throughout this document, references to analyses of corticosteroids refer to analyses of systemic corticosteroids, unless otherwise specified.

Statistical analyses of categorical safety and efficacy endpoints will be descriptive in nature.

Frequency counts and percentages by treatment arm (see [Table JAIM.6.1](#)) will be provided for the safety and efficacy endpoints. For non-model-based efficacy endpoints, 95% confidence intervals (CIs) for single proportions using the Wilson Score (Wilson, 1927; Newcombe, 1998) method will be utilized.

Unless otherwise stated, inferential statistical analyses (p-values and 95% CIs) which compare treatment groups will not be conducted.

For continuous efficacy and health outcomes endpoints the significance of within-treatment group changes from baseline will be evaluated by testing whether the treatment group least squares mean (LS mean) changes from baseline are different from zero; the 95% CI and the standard error for the LS mean change will also be displayed.

Change from baseline (defined in [Section 6.3](#)) will be calculated as the postbaseline (at that visit) value minus the baseline value. If all baseline values are missing for a particular variable, the change from baseline and percent change from baseline will not be calculated.

[Table JAIM.6.1](#) summarizes the treatment arms based on the treatment assigned in JAIM.

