### 6.14.2. Extent of Exposure

Exposure, including total patient-years of exposure, will be calculated for Study JAIM. Duration of exposure to study drug will be summarized using descriptive statistics (n, mean, standard deviation [SD], minimum, first quartile, median, third quartile, maximum). Cumulative

exposure and duration of exposure will be summarized in terms of frequency counts and percentages by category and treatment group.

Total patient-years of exposure (PYE) will be reported for each treatment group for overall duration of exposure. Exposure will also be classified by the frequency of patients falling into different exposure ranges. Exposure ranges will generally be reported in weeks using the following as a general guide:

- $\geq 4$  weeks,  $\geq 16$  weeks,  $\geq 24$  weeks,  $\geq 52$  weeks,  $\geq 84$  weeks, and  $\geq 156$  weeks.
- $>0$  to  $<4$  weeks,  $\geq 4$  weeks to  $<16$  weeks,  $\geq 16$  weeks to  $<24$  weeks,  $\geq 24$  weeks to  $<52$  weeks,  $\geq 52$  weeks to  $<84$  weeks,  $\geq 84$  weeks to  $<156$  weeks, and  $\geq 156$  weeks.

Overall exposure in JAIME will be summarized in total PYE which is calculated according to the following formula:

$$\text{Total PYE} = \text{sum of duration of exposure in days (for all patients in treatment group)} / 365.25$$

Additionally, time spent in the study will be summarized with descriptive statistics (n, mean, SD, minimum, first quartile, median, third quartile and maximum).

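### The JAIM-alone safety tables specify only counts and percentages, although follow-up varies by patient and the protocol provides for incidence rates where they fit

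*SAP*

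**What the plan says.** Protocol 10.3.4 sets the rule: "Categorical safety measures for JAIM alone will be summarized with percentages, and incidence rates where appropriate". It then lists four summaries for JAIM itself: permanent discontinuation due to adverse events, SAEs, temporary interruption, and permanent discontinuation before completion. The statistical paragraph of the protocol synopsis has a similar rule: "The categorical safety measures will be summarized with percentages and incidence rates, where appropriate".

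The SAP narrows this. Section 6.1 promises "Frequency counts and percentages by treatment arm" for safety and efficacy endpoints. In Table JAIM.6.6, which defines the adverse-event output for the JAIM-alone report, every summary with a stated statistic is a count and percentage. For SAEs the row reads "The number and percentage of patients reporting SAEs using MedDRA Preferred Term nested within SOC". The rows on TEAEs, on adverse events that end treatment and on interruptions take the same form. The remaining rows are listings, or overviews whose statistics are not given. The infection overview in 6.14.5 names no rate.

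Patient-years are planned in 6.14.2: "Total patient-years of exposure (PYE) will be reported for each treatment group for overall duration of exposure". The SAP does not use them as a denominator for any safety event. Its only event rate is the annualized flare rate, an efficacy endpoint.

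Under Table JAIM.6.5 the safety window may close at "the cut-off date if subject is on treatment". Disposition and a limit of 30 days off drug also apply, and whichever comes first decides.

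**The concern.** A crude percentage counts every treated patient equally, whether observed for one month or three years. Here observation time differs by design. Treatment lasts up to 156 weeks, patients may stop early, and those still on drug are truncated at a cut-off. Protocol 10.3.6 plans periodic data cuts, and Protocol 7.4 allows a dose arm to be closed by amendment. Two arms with the same underlying risk but different retention would then show different percentages, and a reader of the JAIM report could take the gap for a dose effect or miss a real one.

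The percentages are also hard to set beside the protocol's own safety background. Section 3.3 gives serious infection per 100 patient-years and describes an exposure-adjusted rate for VTE.

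**Working it through.** The plan states no figure to reproduce, so the check is an illustration of how far a crude percentage moves when the true rate does not.

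**Inputs**
- Event rate L = 0.03 per year, from the 3.0 per 100 patient-years for serious infection in the RA program (Protocol 3.3). It is illustrative, not a forecast for SLE.
- Horizon T = 156 × 7 / 365.25 = 2.99 years (treatment period, Protocol 5.1).
- Annual discontinuation rate d: not in the documents. Assumed range 0 to 0.30.
- Both hazards constant, with discontinuation independent of event risk.

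**Formulas**
- Crude proportion: P = L/(L+d) × [1 − exp(−(L+d)T)]
- Mean time at risk, to first event or end of follow-up: R = [1 − exp(−(L+d)T)]/(L+d)
- Incidence rate: P/R = L

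**Two arms at equal risk**
- d = 0.05: P = 0.03/0.08 × [1 − exp(−0.239)] = 0.375 × 0.213 = 8.0%. R = 0.213/0.08 = 2.66 years.
- d = 0.30: P = 0.03/0.33 × [1 − exp(−0.987)] = 0.0909 × 0.627 = 5.7%. R = 0.627/0.33 = 1.90 years.
- The percentages differ by 2.3 points, a ratio of 1.4. The incidence rate is 3.0 per 100 patient-years in both.

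**Across the assumed range**

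| d per year | Crude % | Rate per 100 PY |
|---|---|---|
| 0 | 8.6 | 3.0 |
| 0.05 | 8.0 | 3.0 |
| 0.10 | 7.4 | 3.0 |
| 0.20 | 6.5 | 3.0 |
| 0.30 | 5.7 | 3.0 |

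At an assumed 10 per 100 patient-years, d = 0.05 and d = 0.30 give 24.1% and 17.4%, again a ratio of about 1.4.

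**Truncation by a cut-off, no drop-out.** P = 1 − exp(−Lt) gives 2.9% if everyone is cut at Week 52 and 8.6% at Week 156, at the same rate of 3.0.

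**Would the planned patient-years serve as the denominator?** The 6.14.2 total sums drug exposure and does not stop at the first event. If patients stay on drug after an event, mean exposure is 2.78 years at d = 0.05 and 1.97 years at d = 0.30. At a true rate of 3.0, 8.0/2.78 and 5.7/1.97 both give about 2.9 per 100 patient-years, which is close. At a true rate of 10, 24.1/2.78 = 8.7 and 17.4/1.97 = 8.8, which is too low. Exposure also leaves out the off-drug window of up to 30 days in which events still count under Table JAIM.6.5.

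**The case against.** The strongest objection is that nothing has been breached. The protocol leaves rates to judgement, and its four JAIM-specific items are worded as patients with an event. That stands: a reader might infer that the protocol demands a rate for each of these summaries, and it does not. What remains is that the SAP supplies no safety rate and gives no reason, in a study whose observation time varies by design.

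Second, a reader might infer that the primary objective is left without exposure-adjusted results. The documents do not support that. Protocol 10.3.4 assigns the primary safety endpoints to the integrated analysis, and SAP 6.14 and 6.14.5 repeat the referral. That plan was not supplied and may contain rates. The SAP does not, however, say that it will provide rates for JAIM alone.

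Third, the primary endpoints are worded as proportions, so percentages belong in the tables. This stands, and the percentages should stay.

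Fourth, no document gives retention by arm. All arms share one schedule, dose assignment is blinded, and 6.1 rules out between-arm inference unless otherwise stated. A reader might assume a much wider exposure gap and a larger distortion, but nothing in the documents supports one. The contrast across data cuts is also weaker for this table, because 6.1 ties the SAP to the primary outcome lock and puts earlier outputs in a separate list.

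Fifth, patient-years are printed by arm, so readers can form a rough rate. For uncommon events that works well, as shown above; for commoner events it understates the rate.

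Finally, a JAIM-only rate would not make all arms comparable. Continuing patients have already completed a 52-week study on drug, while former placebo patients are new starters. Rates remove the dependence on length of follow-up, not that difference.

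**Conclusion.** The point holds for the JAIM-alone report tables. Followed exactly, the SAP yields percentages that depend on exposure, while the protocol provides for rates where appropriate and the exposure data are already planned by arm. In the illustration, equal risk of 3.0 per 100 patient-years shows as 8.0% against 5.7%. That rests on constant hazards, independent drop-out, an event rate borrowed from RA, and assumed discontinuation of 0.05 and 0.30 per year. It shows that an artefact of this size is possible, not that one will occur. The gap is worth closing because the remedy is cheap. It does not show that the program's primary safety analysis is deficient.

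**What to change.** Keep every planned percentage. In Table JAIM.6.6 and the infection overview, add patients with a first event per 100 patient-years at risk, with 95% CI, by arm and for pooled baricitinib, for:
- SAEs
- adverse events leading to permanent discontinuation
- temporary interruptions
- serious infections, herpes zoster and opportunistic infections.

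Rates for all TEAEs by preferred term are not needed. In Phase 2, 71.4% and 73.1% of baricitinib patients had a TEAE within 24 weeks (Protocol 3.3), so a first-event rate for so frequent an outcome adds little.

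Define time at risk as first JAIM dose to first event or the end of the Table JAIM.6.5 postbaseline period, whichever is earlier. Do not reuse the 6.14.2 total, which neither stops at first event nor covers the off-drug window. Interruption cannot occur after the last dose, so state whether off-drug days count for it.

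If the integrated plan already supplies JAIM-alone rates for these events, a sentence in SAP 6.14.1 citing it would be enough. The cost is a time-at-risk derivation for each event category and wider tables; no new data are needed.

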Investigators are not obligated to actively seek AEs or SAEs in subjects once they have discontinued and/or completed the study (the patient disposition CRF has been completed). However, if the investigator learns of any SAE, including a death, at any time after a subject has been discharged from the study, and he or she considers the event reasonably possibly related to the study treatment or study participation, the investigator must promptly notify Lilly.

9.2.1.1. **Suspected Unexpected Serious Adverse Reactions**

Suspected unexpected serious adverse reactions (SUSARs) are serious events that are not listed in the IB and that the investigator identifies as related to investigational product or procedure. United States 21 CFR 312.32 and European Union Clinical Trial Directive 2001/20/EC and the associated detailed guidances or national regulatory requirements in participating countries require the reporting of SUSARs. Lilly has procedures that will be followed for the

identification, recording and expedited reporting of SUSARs that are consistent with global regulations and the associated detailed guidances.

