9.4.8. Safety Monitoring

Lilly will periodically review evolving aggregate safety data within the study by appropriate methods.

The Lilly-designated medical monitor will monitor safety data throughout the course of the study. Lilly will review SAEs within time frames mandated by company procedures. The Lilly-designated medical monitor will, as is appropriate, consult with the functionally independent Global Patient Safety (GPS) therapeutic area physician or clinical scientist and periodically review trends in safety data and laboratory analytes. Any concerning trends in frequency or severity noted by an investigator and/or Lilly or its designee may require further evaluation.

All deaths and SAE reports will be reviewed in a blinded manner by Lilly during the clinical trial. These reports will be reviewed to ensure completeness and accuracy, but will not be unblinded to Lilly during the clinical trial. If a death or clinical AE is deemed serious, unexpected, and possibly related to investigational product, only Lilly GPS will be unblinded for regulatory reporting and safety monitoring purposes. These measures will preserve the integrity of the data collected during this trial and minimize any potential for bias while providing for appropriate safety monitoring.

Investigators will monitor vital signs and carefully review findings that may be associated with cardiovascular events. Adverse event reports and vital signs will be collected at each study visit. The cardiovascular monitoring plan includes the following:

- Regular monitoring of lipid levels
- Potential MACE (cardiovascular death, myocardial infarction, stroke), other cardiovascular events (such as, hospitalization for unstable angina, hospitalization for heart failure, serious arrhythmia, resuscitated sudden death, cardiogenic shock, coronary interventions), venous thrombotic events and noncardiovascular deaths will be identified by the investigative site or through medical review and will be sent to a blinded Clinical Event Committee for adjudication at regular intervals.

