### **6.14.3. Clinical Laboratory Evaluation**

For the categorical analysis, the analysis period is defined as the treatment period plus up to 30 days off-drug follow-up time. The analysis period for the continuous by-visit analyses (eg, change from baseline by visit) is defined as the treatment period excluding off-drug follow-up time. Refer to the iSAP for more details. The following analyses are planned:

- clinical laboratory evaluation in terms of box plots and treatment-emergent summaries.

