### **6.14.5. Special Safety Topics, Including Adverse Events of Special Interest**

Special safety topics will be analyzed in the context of combining the safety data from the originating Studies JAHZ and JAIA with the safety data from Study JAIME. The planned analyses are described in the ISAP.

For the purposes of the CSR for Study JAIME alone, the summaries of infections and type of infections will be provided.

The following summaries for each treatment group will be included in the overview of infections:

- patients with  $\geq 1$  treatment-emergent (TE) infection
- serious infections
- AEs that led to
  - permanent discontinuation from study drug, and
  - temporary interruption from study drug
- TE opportunistic infection
- TE herpes zoster
- TE herpes simplex
- TE tuberculosis, and
- TE viral hepatitis.

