### **6.19. Clinical Trial Registry Analyses**

Additional analyses will be performed for the purpose of fulfilling the Clinical Trial Registry (CTR) requirements.

Analyses provided for the CTR requirements include the following:

- Summary of AEs, provided as a dataset which will be converted to an XML file. Both SAEs and ‘Other’ AEs are summarized by treatment group and by MedDRA PT.
- An AE is considered ‘Serious’ whether or not it is a TEAE.
- An AE is considered in the ‘Other’ category if it is both a TEAE and is not serious. For each SAE and ‘Other’ AE, for each term and treatment group, the following are provided:
  - the number of participants at risk of an event
  - the number of participants who reported each event term
  - the number of events experienced.

Consistent with [www.ClinicalTrials.gov](http://www.ClinicalTrials.gov) requirements, ‘Other’ AEs that occur in fewer than 5% of patients/subjects in every treatment group may not be included if a 5% threshold is chosen (5% is the minimum threshold).

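### SAP 6.14.1 stops counting TEAEs at the last visit date, Table JAIM.6.5 has no such limit, and the SAP does not say which governs

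*SAP*

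**What the plan says.** SAP 6.14.1 defines a treatment-emergent adverse event (TEAE) as one that begins or worsens after the first JAIM dose and "on or prior to the last visit date during the analysis period". Its next sentence sets the analysis period as the treatment period plus at most 30 days off drug.

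SAP Table JAIM.6.5 defines the safety postbaseline period for every analysis other than the by-visit continuous ones. The period ends at the earliest of three dates:

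- "30 days after last dose date of study drug";
- the study disposition date;
- the cut-off date, for a patient still on treatment.

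In that table the last visit is a limit only for by-visit continuous data: "Includes planned/scheduled measurements after first dose of baricitinib up to last visit, excluding the follow up visit".

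SAP 6.14.3 reads: "For the categorical analysis, the analysis period is defined as the treatment period plus up to 30 days off-drug follow-up time". SAP 6.14.4 says the same for vital signs. Neither adds a last-visit limit. Protocol 10.3.4.1 counts TEAEs from baseline and gives no end date.

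**The concern.** A TEAE table is not a by-visit continuous analysis, so Table JAIM.6.5 and 6.14.1 both apply to it. The 6.14.1 window lies inside the table's period, and the last-visit clause is the only real difference. An event recorded after the last attended visit but before the table's end date is a TEAE if the table's period governs, and is not one under 6.14.1. Nothing in the SAP or protocol gives either precedence.

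The patients who could be affected are:

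- those who die or stop without an early termination (ET) visit;
- those who miss Visit 801 and have a later disposition date;
- those on treatment at a data cut, if the analyses run before the primary lock use this definition.

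At stake is consistency within one report. A recorded fatal infection could appear in the death listing, the SAE displays and the serious-infections row, yet be absent from the TEAE table and from the row for at least one treatment-emergent infection.

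**Working it through.** The plan gives no figure to reproduce. The check is day arithmetic on the two end dates:

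gap = end of the Table JAIM.6.5 period − last visit date admitted by 6.14.1.

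**Inputs.** Visit 801 is due 28 ± 5 days after last dose, so days 23 to 33 (Protocol Table JAIM.1, footnote b). Scheduled visits are 168 days apart from Week 60, with ±14-day windows from Week 84 (Protocol Table JAIM.1; SAP 6.3). Enrolment is about 1100 (Protocol 5.2).

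**Off-drug gap**, with Visit 11/ET taken to fall at last dose:

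| Case | Disposition on that visit date | Disposition on or after day 30 |
|---|---|---|
| Visit 801 on day d, 23 to 30 | 0 days | 30 − d = 7 down to 0; mean 28/8 = 3.5 |
| Visit 801 on days 31 to 33 | up to 30, or 0 | up to 30, or 0 |
| Visit 801 missed, last visit Visit 11/ET | 0 days | up to 30 |

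The second row depends on how 6.14.1 is parsed. If the phrase about the analysis period qualifies the visit, a Visit 801 on days 31 to 33 lies outside the period and the limit falls back to Visit 11/ET. If it qualifies the event, nothing is lost. The mean of 3.5 weights the eight days equally.

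**On-drug gap.** Consecutive late visits can be 168 + 14 + 14 = 196 days apart. A patient who dies or stops without an ET visit can therefore have an on-drug gap approaching 196 days. The documents do not say how many patients this will be.

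**Off-drug scale if every patient had the largest gap.** 1100 × 30/365.25 = 90 patient-years, and 30/(1092 + 30) = 2.7% of the period.

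- At 3.0 serious infections per 100 patient-years (the rheumatoid arthritis rate in Protocol 3.3; using it for lupus is an assumption), 90 × 0.03 = 2.7 events. With a 2-day gap the figures are 6 patient-years and 0.2 events. This is for scale only, since the serious-infections row is not worded as treatment-emergent.
- Protocol 3.3 gives 73.1% with a TEAE at 24 weeks on 4 mg. As a constant hazard (assumption), −ln(1 − 0.731)/24 = 0.0547 per week, so 1 − exp(−0.0547 × 156) exceeds 99.9% by Week 156. Thirty more days add less than 0.01 percentage points, or 0.7 points at a quarter of that hazard.

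**Data cut, illustration only.** The visit intervals are 4, 8, 12 (four times) and 24 (four times) weeks. With patients spread evenly over Weeks 0 to 156 (assumption), mean time since last visit is Σ(interval²)/(2 × 156) = 2960/312 = 9.5 weeks. That is 9.5/78 = 12% of accrued time. At the same rate it is 6 of 49 serious infections. This is an upper bound, because many events after the last visit are not yet recorded at a cut.

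**Displays that depend on TEAE status.**

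- The TEAE table in Table JAIM.6.6.
- Six of the nine rows of the infection overview in 6.14.5.
- The registry data in 6.19, where an event falls in the 'Other' "category if it is both a TEAE and is not serious".
- Possibly the Overview of AEs, whose contents are not specified.

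**The case against.** The strongest reply is that 6.14.1 is the only SAP text that actually defines a TEAE. On that view a specific definition narrows a general period, so events after the last visit do have a rule: they are not TEAEs. This disposes of one inference a reader might draw, that such events are left with no rule at all. It does not settle precedence, because Table JAIM.6.5 expressly covers every analysis except the by-visit continuous ones.

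Second, the contrast with laboratory values and vital signs is weak. Those are obtained essentially at visits, so a last-visit limit there would be largely redundant. That stands, and the point does not rest on it.

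Third, the rules largely agree on the planned path. All patients should return for Visit 801, and if disposition is dated at a Visit 801 on or before day 30 the gap is zero. Protocol 9.2.1 releases investigators from actively seeking events in patients "once they have discontinued and/or completed the study (the patient disposition CRF has been completed"), which suggests a form date close to the last contact. The SAP, however, does not define the study disposition date.

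Fourth, Protocol 9.4.8 says: "Adverse event reports and vital signs will be collected at each study visit". Most non-serious events after a final visit will therefore not be recorded under either rule. Those reported between visits are mainly SAEs and deaths through the 24-hour route in Protocol 9.2.1. Their displays are not worded as limited to TEAEs, and the registry counts an SAE whether or not it is a TEAE. This is the main reason to expect a small effect.

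**Conclusion.** The conflict is real and worth resolving, because TEAE is a named primary-endpoint term and two programmers following the SAP could get different counts. Any error runs one way: the last-visit clause can only remove events. For the final JAIM-alone report the effect is probably small. The number of events cannot be estimated, because the documents do not give the frequency of missing ET or Visit 801 visits, or the dating of disposition.

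Three stronger readings are not supported.

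- A reader might infer that the primary safety result is biased. Protocol 10.3.4 and SAP 6.14 place the primary safety analysis in the integrated plan, which is not among the documents, so its TEAE window is unknown.
- A reader might take the 12% data-cut figure as the size of the problem. SAP 6.1 limits this plan to the report at primary outcome lock and leaves pre-lock analyses to a separate list. Periodic cuts are planned (Protocol 10.3.6) and SAP Appendix 2 has an Interim 1 column, but whether those analyses use this definition is not stated.
- A reader might infer that deaths or SAEs would disappear from the report. They would remain in their own displays. The problem is inconsistency with the TEAE displays.

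**What to change.** First check the TEAE end date in the integrated safety plan. Then use one end date in both 6.14.1 and Table JAIM.6.5.

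The preferred wording removes the last-visit clause from 6.14.1: *a TEAE is an event that first occurs or worsens in severity after the first JAIM dose and within the Table JAIM.6.5 postbaseline period for analyses other than by-visit continuous ones.* Recorded on-treatment events and those up to 30 days off drug would then count, subject to that table's disposition and cut-off limits. The ambiguity over a Visit 801 on days 31 to 33 would also go.

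If the integrated plan carries the same last-visit clause, change both documents together so that JAIM-alone and integrated counts agree.

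Also define the study disposition date, and state that the treatment-emergent infection rows, the registry 'Other' events and any TEAE content of the Overview of AEs use this window.

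The cost is one sentence, one definition and a check against the integrated plan, plus a matching edit there if needed. No new data are required. TEAE counts would stay the same or rise slightly. If outputs have already been programmed with the clause, the TEAE flag must be re-derived and the dependent displays rerun.
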